The subject will serve as her own control for the study. Imagio OA evaluation results will be compared with the Imagio ultrasound component (IUS) for the registration read and Imagio will also be assessed in combination with Mammography and conventional diagnostic ultrasound (CDU) image sets for the reimbursement reads. The ultrasound component of Imagio, designated IUS, will serve as the "internal control." If a biopsy is performed, then the histology will serve as the gold standard; if a biopsy is not performed at study entry or for 12 months following study entry with no change in the target mass according to CDU (if performed), then the subject is considered to be a True-Negative for analysis purposes as confirmed by the Truth Panel.

Study Duration:

The duration of study participation for each subject will be up to 12 months depending on the screening BI RADS score and decision to biopsy. The duration of the entire study, from first subject enrolled until the last subject last visit is anticipated to be 24 months.

Table 1: SCHEDULE OF EVENTS

Evaluation	Screening Visit	Enrollment Visit Day 1	Imaging Visit Day 1-10	First Biopsy (within 12 Months)*	Follow-up for Subjects with No Biopsy (12 Months +/- 30 days)**
Informed Consent		Х			
I/E Criteria		X##			
Demographics/ Medical History		Х			
BI-RADS Score (including density)	Х				
Conventional Diagnostic Ultrasound	Х				
Biopsy Decision	Х				
Mammogram	X#				
Imagio Evaluation			Χ*	X**+	X**+
Subject Completed Survey			Χ		
Directed Breast History			Х		
Adverse Event Evaluation		Х	Х	Х	Х
Histopathology Assessment				Х	Х
Histopathology Report				Х	Х
Past Imaging Studies		Х			

[#] Subjects may have a mammogram at investigator discretion.

Subjects must have a conventional diagnostic ultrasound and all other diagnostic tests completed and decision to biopsy made before the Enrollment Visit.

- * Subjects who are scheduled to have a biopsy at any time during the 12 month Follow-Up (including baseline) will have an Imagio evaluation of the breast mass within 45 business days prior to the biopsy; for subjects requiring a second biopsy, additional time (up to 45 business days) will be permitted to perform the second biopsy if a waiver is granted by the study Medical Monitor, but a second Imagio Evaluation is not performed.
- ** Optional 6 month (+/- 30 Days) Follow-Up Visit at investigator discretion and planned 12 month Follow-Up Visit if no biopsy is performed within 12 months of Enrollment Visit.

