In the absence of new findings, the decision to not recommend a biopsy during the first 12 months will be regarded as evidence of no disease, True Negative (TN) for those not biopsied; this is in accordance with FDA guidance regarding study analysis conventions. The study design will evaluate the specificity as the primary effectiveness endpoint and the sensitivity as secondary effectiveness endpoint for comparing Imagio relative to the pre-biopsy conventional diagnostic ultrasound images and histology results (if biopsy is performed). To ensure consistency, the assessment of all imaging studies including Imagio will be managed by an independent Imaging Coordination Committee (ICC) to coordinate the pool of potential readers for the Pilot/Pivotal Study and the subset of 7 qualifying readers for the Pivotal Study in accordance with FDA MRMC imaging review guidelines. Each registration reader will independently evaluate both image sets per subject once all imaging data are available per subject.

In addition, a Truth Panel will consist of at least two independent expert radiologists and a Histopathologist; the Truth Panel will work closely with the Sponsor and/or designee to adjudicate all cases and to review anomalies relating to pathology, imaging, subject history, and clinical course for the additional purpose of alerts regarding subjects at risk for malignancy, but not biopsied.

The major anticipated advantages of co-registered OA and B-mode imaging are as follows:

- 1. High optical contrast between potentially malignant and benign tissues that results from enhanced density of the microcirculation network within and around masses and enhanced thermo-elastic expansion coefficient in potentially malignant masses;
- 2. High sensitivity of detection due to efficient opto-thermal generation of pressure in masses, and sensitive detection of resulting ultrasonic waves with novel piezoelectric arrays; and
- 3. High (≤1 mm) spatial resolution that results from pulsed laser excitation and time-resolved detection of ultrasonic signal profiles with array detectors;
- 4. Substantial depth of monitoring (up to 8 cm in tissue phantoms) that results from deep penetration of the near-infra-red photons in tissues, efficient conversion of laser energy into acoustic pressure waves propagating through the breast, with negligible attenuation and minimal distortion, and from high sensitivity of piezoelectric arrays; and

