- Diagnostic referral to assess focal physical symptoms and / or signs that were either a chief complaint of the subject or were elicited by the healthcare practitioner (excluding focal breast pain in the absence of other positive clinical findings).
- Interval Clinical Problems (symptoms or physical findings excluding isolated focal breast pain, that have developed between yearly mammograms).
- Other referrals to diagnostic conventional ultrasound including subjects younger than 30 years old for a clinically suspicious area, or subjects referred from a screening MRI because of an

abnormality.

These subpopulations will be analyzed in aggregate as well as individually.

The Imagio diagnostic ultrasound component will serve as the "internal control".

The specificity determined by a 2% POM is the primary effectiveness endpoint while the sensitivity is the secondary effectiveness endpoint.

Multiple effectiveness endpoints will be assessed (one primary and four secondary) so the overall 5% Type I error will be controlled by requiring two-sided p=0.01 to establish statistical significance. Specificity will be tested first according to a superiority test while sensitivity will then be tested according to non-inferiority tests. Testing will be based on the specificity (primary endpoint) and sensitivity (secondary endpoint), both based on a 2% Probability of Malignancy (POM). The overall specificity exceeding 40% will also be tested. In addition, downgrading benign masses and upgrading malignant masses using Imagio relative to the site and relative to IUS will be evaluated.

The superiority test and the non-inferiority tests will each have at least 80% power to test their respective hypotheses according to a two-sided test with overall 1% Type I error. The histopathology findings of the biopsy procedure will serve as a gold standard for Imagio. The decision to not recommend a biopsy during the first 12 months together with a negative 12 month clinical and imaging follow-up and no evidence of a >20% increase in the mass will be regarded as evidence of no disease (True-Negative for a negative OA/FN for a positive screening OA) for those initially not recommended for biopsy.

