8.3. Analysis Populations

Seno Clinical Study Protocol: PIONEER-01
300176 Rev 8 PIONEER 01 Protocol Amendment 3.2

Confidential Page 54 of 80

All analyses will be performed with the intention to diagnose (ITD) study population which consists of all subjects coming in for their scheduled Imagio evaluation, having Imagio data declared evaluable, and having a biopsyat 12 months, or declared to be TN (or FP) at 12months.

There will be Truth Panel review to identify mass-specific subgroups and TN outcomes as well as reader-specific exclusions for the following:

- 1. Cases with QAR concerns (including cases with previously unidentified suspicious masses and cases where the Imagio evaluation was incomplete, unreliable, or unusable) for exclusions
- 2. Cases where the number or numbering of suspicious masses is under dispute (per QARs or IRs) for exclusions
- 3. Cases with questionable eligibility for exclusions
- 4. Cases with high risk histologies for separate analyses
- 5. Cases where individual IRs identified problems with specific image sets for exclusions
- 6. Cases with NDUs to determine if a mass was a True-Negative (TN) for specificity calculations.

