8.5. Analysis Definitions

The final data for diagnostic test sensitivity and specificity will be presented in terms of a 2×2 table as follows; the threshold for defining a positive POM will be 2% corresponding to clinical practice standards:

Table 5: 2 x 2 Table

	Cancer	Benign
Test +	True Positive (TP)	False Positive (FP)
Test -	False Negative (FN)	True Negative (TN)

The above 2x2 table will also be constructed separately for Imagio and the Imagio diagnostic ultrasound component relative to a cancer or benign diagnosis. In addition, these 2x2 tables will also be generated for immediate biopsies, for delayed biopsies, for all biopsies, and for all cases including those not biopsied; discordant pairs for sensitivity as well as specificity will be analyzed. Those subjects without a biopsy will be excluded if they were not followed without a subsequent clinical evaluation.

A subject will be assigned to a row in the table depending on the respective diagnostic test result. Subjects with a diagnosis (biopsy or 11 month follow-up with no biopsy) will be assigned a column in the table according to the following rules:

- 1. If the result of the biopsy results in a cancer diagnosis, then the subject will be assigned to the Cancer column.
- 2. If the result of the biopsy results in a benign diagnosis, then the subject will be assigned to the Benign column.
- 3. If the biopsy was not performed and the subject was evaluated after 11 months post-baseline (nominal 12 month evaluation), then the subject will be counted as TN as long as there were no contrary clinical or radiologic findings (not to be based on Imagio); any mass declared to have any contrary clinical or radiologic findings will be declared to be a False-Positive if the Imagio POM was ≤2%; otherwise the subject will not be included in the table
- 4. If the baseline Imagio evaluation was not performed or declared to not be useable, then the subject will not be included in the table.

In addition, the cancer group will be further divided into invasive carcinoma and DCIS categories and each of these two categories will be assessed separately within a 2x2 table.

The use of the terms *sensitivity* and *specificity* is justified in this study because the biopsy and 11 month evaluation (12 month nominal evaluation) is the gold standard. The following statistical endpoints will be assessed for each image set:

- The true positive rate (TPR) or sensitivity of the test is defined as TP/ (TP + FN)

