- The specificity of the test is defined as TN/ (TN + FP)
- The concordance of the test is defined as (TP + TN)/N
- The positive likelihood ratio is defined as TPR/FPR
- The negative likelihood ratio is defined as (1 TPR)/(1 FPR)
- The positive predictive value (PPV) is defined as TP/(TP + FP)
- The negative predictive value (NPV) is defined as TN/ (TN + FN)
- The *odds ratio* (OR) is defined as (TP/FP)/(FN/TN)

Given that biopsy decisions are made using the 2% POM, POM levels >2% have limited relevance to the 2% threshold now widely used for making biopsy decisions.

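### Protocol 8.1.1 labels a disease-free, unbiopsied mass with a positive scan FN where Table 5 and 8.3 make it FP; 8.5 rule 3 does not repair this, and the true-negative condition differs between sections

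*Protocol*

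**What the plan says.** **Cell labels.**
- Section 8.1.1, on masses not initially recommended for biopsy that meet its follow-up conditions: "evidence of no disease (True-Negative for a negative OA/FN for a positive screening OA".
- Section 8.5, Table 5, puts FN in the cancer column and FP in the benign column. The formulas follow: "sensitivity of the test is defined as TP/ (TP + FN" and "The specificity of the test is defined as TN/ (TN + FP". A reading is positive above a 2% POM.
- Section 8.3 admits an unbiopsied mass to the analysis population if it is "declared to be TN (or FP" at 12 months. FN is not an option there.
- Section 8.5, rule 3: an unbiopsied subject evaluated after 11 months is "counted as TN as long as there were no contrary clinical or radiologic findings (not to be based on Imagio". With contrary findings, a mass with an Imagio POM of 2% or less becomes a False-Positive; otherwise it is left out of the table.

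**Condition for a true negative without biopsy.**
- Synopsis, Control: "with no change in the target mass according to CDU (if performed), then the subject is considered to be a True-Negative for analysis purposes", followed by confirmation by the Truth Panel.
- Section 3.3: "the decision to not recommend a biopsy during the first 12 months will be regarded as evidence of no disease", qualified by the absence of new findings.
- Section 6.2.5: no biopsy recommended at Month 12 and no new symptoms, physical findings or imaging abnormalities, subject to the Truth Panel.
- Section 8.1.1: no biopsy recommended, "together with a negative 12 month clinical and imaging follow-up and no evidence of a >20% increase in the mass".
- Section 8.1.1, further on: no biopsy recommended in the first 12 months, with no imaging or growth condition.

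**The concern.** Unbiopsied masses are a planned group (section 6.2.2), and those judged disease-free enter the benign column on which the primary endpoint is computed. If one of them is read positive, it is a false positive and must count against specificity. Labelling it FN takes it out of the specificity denominator and adds it to the sensitivity denominator as a missed cancer. The first shift favours the device on the primary endpoint; the second works against it on the secondary endpoint.

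Section 8.1.1 names OA only. If IUS is scored by Table 5, the same mass would count in the benign column for one image set and the cancer column for the other, which breaks the paired comparison. Separately, the Truth Panel has no single written condition for calling an unbiopsied mass negative.

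**Working it through.** **1. One mass, three cells.** Take an unbiopsied mass with clean follow-up, read with POM above 2%.

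| Source | Cell |
|---|---|
| 8.1.1 parenthesis | FN |
| 8.5 rule 3 | TN |
| Table 5 with 8.3 | FP |

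Only FP fits the 2×2 table. Now take an unbiopsied mass with contrary findings and POM of 2% or less. Rule 3 calls it a False-Positive, but a test-negative mass can only be FN or TN in Table 5. With POM above 2% the same mass is dropped, so its place in the table depends on the reading.

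**2. The plan's own figures.** No stated figure is in dispute, but two design figures depend on this classification, and both reproduce by exact binomial. Table 8 (N = 1,160, 40% against 45%, one-sided 0.5%) rejects at 508 or more, with size 0.0047 and power 80.4%, stated 80%. Table 9 (N = 360, 90% against 95%) rejects at 339 or more, with size 0.0034 and power 80.4%, stated 80%.

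**3. Size of the 8.1.1 relabelling if applied literally.** From the protocol: at least 1,000 benign masses (3.1), sensitivity expected to be at least 95% (8.2.2), alternative specificity 45% (Table 8). Assumed, because the protocol does not give them: 400 cancers, unbiopsied share u of benign masses 5–20%, positivity q among those 25–55%.

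True cells: TN = 450, FP = 550, TP = 380, FN = 20. Masses moved: m = 1,000 × u × q. Apparent Sp = 450/(1,000 − m); apparent Se = 380/(400 + m).

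| u | q | m | Sp | Se |
|---|---|---|---|---|
| 5% | 25% | 12.5 | 45.6% | 92.1% |
| 5% | 55% | 27.5 | 46.3% | 88.9% |
| 10% | 25% | 25 | 46.2% | 89.4% |
| 10% | 55% | 55 | 47.6% | 83.5% |
| 20% | 25% | 50 | 47.4% | 84.4% |
| 20% | 55% | 110 | 50.6% | 74.5% |

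**4. Against the design values.**
- Sensitivity: 420 cancers (Table 7) at 95% give 399 true positives. Moving 24 masses gives 399/444 = 89.9%, a fall of 5.1 points against a 5-point margin.
- Specificity: 1,160 benign masses at the 40% null give 464 true negatives. Moving 2%, 5% or 10% gives 464/1,136.8 = 40.8%, 464/1,102 = 42.1% or 464/1,044 = 44.4%. The one-sample exact test of Table 8 would then reject falsely about 2%, 12% or 61% of the time, against a planned 0.5%.
- If the label is applied to OA only and both true specificities are 40%, the same moves create an apparent Imagio advantage of 0.8, 2.1 or 4.4 points.

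**5. The true-negative condition.** Two differences remain after reading the sections together.
- Imaging: the synopsis asks for an unchanged mass on CDU only if CDU was done, and the later sentence in 8.1.1 asks for no imaging, while the earlier sentence in 8.1.1 requires negative imaging follow-up. The footnotes to Tables 1 and 3 leave diagnostic imaging at follow-up to the investigator, and rule 3 bars Imagio as evidence. A mass with no follow-up imaging other than Imagio can therefore meet one condition and fail another.
- Growth: the synopsis asks for no change, while 8.1.1 tolerates growth up to 20%. A mass that grew 15% fails the first, read strictly, and meets the growth limit of the second.

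**The case against.** The FN label is a single parenthesis in a strategy section. Table 5, the formulas and 8.3 all point to FP, and the same sentence in 8.1.1 calls the mass disease-free, so FN is most naturally a slip. The lead-in to the rules in 8.5 also says that the test result fixes the row, which is the right principle. A literal application would show itself, because sensitivity would fall visibly below the expected 95%. All of that stands, and it makes the numerical damage conditional. It does not remove the error: rule 3 departs from its own lead-in, and a programmer following either 8.1.1 or rule 3 as printed fills wrong cells.

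Positivity of 55% is only one minus the assumed overall specificity. The Unbiopsied Group is BI-RADS 3 or at most 2% POM by the investigator (6.2.2), so its positivity is plausibly lower. This stands, and it is why the range starts at 25%.

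On the true-negative condition, a reader might infer that every section conflicts with every other. The documents do not support that. Sections 3.3, 6.2.5 and 8.5 are broadly compatible. The 20% limit could be meant to define what counts as change. Section 8.5 excludes unbiopsied subjects without later clinical evaluation, and 11 against 12 months is no conflict given the visit window of ±30 days. Truth Panel review recurs throughout, and a detailed criterion may sit in a document not shown. What remains is the imaging requirement and the growth wording, where the protocol itself says different things.

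**Conclusion.** Wrong as written. The FN label in 8.1.1 contradicts the protocol's own 2×2 table, formulas and analysis population, and rule 3 of 8.5 adds two mislabels of its own. A reader might go further and conclude that the sensitivity and specificity results will be corrupted. The documents do not show that; the shift arises only if 8.1.1 is applied literally.

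In that case, under the stated assumptions, specificity would read 45.6–50.6% instead of 45%, and sensitivity 92.1–74.5% instead of 95%. The unbiopsied share, its positivity and the 400 cancers are assumptions. The false-rejection rates apply to the one-sample test of Table 8, not to a model pooled over seven readers.

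The inconsistency in the true-negative condition is real but narrow. It cannot be sized, because the protocol gives no count of masses on which the versions would disagree.

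**What to change.** 1. In 8.1.1, change FN to FP for a disease-free mass with a positive reading.
2. Rewrite 8.5 rule 3 so that the reference standard assigns only the column, and each reader's POM at the 2% threshold assigns the row, identically for Imagio and IUS.
3. Correct the contrary-findings clause so that a mass with POM of 2% or less is not called FP, and so that keeping or dropping such a mass does not depend on the reading.
4. Have the sponsor reconcile the true-negative wording in the synopsis, 3.3, 6.2.5, 8.1.1 (both places) and 8.5 into one definition for the Truth Panel, settling the imaging requirement and the mass-change criterion. Which follow-up or growth rule to adopt is the sponsor's decision; this review proposes none.

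Items 1 to 3 cost wording only, with no new data or rereads. Item 4 is also wording, but depending on the definition chosen, a few unbiopsied masses may become non-evaluable.

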- **5.1.5** Software: The software controls the overall data flow from the data acquisition process to the display of the final co-registered OA and diagnostic ultrasound images. The system continuously acquires both OA data from the dual lasers and diagnostic ultrasound images from the diagnostic ultrasound subsystem. Ancillary data such as the physician annotations are stored and saved in DICOM format.

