5.8. Standard Diagnostic Measure (SDM) as Comparator

The diagnostic ultrasound of Imagio will serve as the "internal control". The conventional diagnostic control will service as the "external control"; the CDU must be completed within 45 business days prior to the Screening Visit and interpreted before the Enrollment Visit. If a biopsy is to be performed during the first 12 months, then any planned biopsy during the first 12 months must be scheduled to take place within 30 business days after the Imagio evaluation. The histologic findings of the biopsy procedure will serve as a gold standard for Imagio and the decision to not perform a biopsy during the first 12 months will be regarded as evidence of no malignant disease for those not biopsied, subject to review by the Truth Panel. Subjects requiring a second biopsy will be allowed additional time (up to 45 business days) to undergo a second biopsy.

The presented study design will evaluate all images that contribute to the decision to either perform a biopsy or to follow the subject for up to 12 months; this includes mammography will be read alone and in combination with conventional diagnostic ultrasound and Imagio which will be separately read by the reimbursement readers. The registration readers will focus on the IUS and Imagio image sets to be read in the following pre-defined order:

- 1. Imagio diagnostic ultrasound alone (IUS)
- Imagio (diagnostic ultrasound plus opto-acoustics [OA]).

Specific image sets may include screening and diagnostic mammography as well as other diagnostic images but excluding the optional color or power Doppler. The images will be received, assigned, sent, recorded, and received back by the Imaging Coordination Committee. The ICC will manage the image set review process by the independent readers. To preserve their independence and objectivity as well as to minimize bias, the independent readers will NOT have access to any clinical data, any decisions to biopsy, or to any biopsy outcomes.

The Medical Monitor will be contacted regarding any biopsied cases where it is unclear whether the correct site was biopsied as well as have access to all unbiopsied cases where the QA evaluators or the

Seno Clinical Study Protocol: PIONEER-01 300176 Rev 8 PIONEER 01 Protocol Amendment 3.2

Confidential Page 36 of 80

independent readers identified a new suspicious mass with a high probability of malignancy to be conveyed to the respective site investigator.

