A total of 7 independent radiologists will be assigned per each case to independently evaluate both image sets (IUS and Imagio) per subject. In addition, 3 other independent readers will perform the reimbursement reads. All independent readers will evaluate all Pivotal Study cases; the readers will also review 5% of all cases to assess temporal trends and consistency; the initial evaluation will be used in all analyses.

Each registration reader will review the data from the two image sets (IUS, Imagio) for each case; each reader will evaluate Imagio according to a pre-determined diagnostic rule set based on OA image characteristics and will similarly evaluate IUS according to another pre-determined diagnostic rule set and each reader will estimate the probability that the mass is cancer on a scale from 0% to 100% in 5% increments (1% if \leq 10% or \geq 90%). Readers will assess IUS and Imagio in this pre-defined order during independent review sessions; this pre-defined order is consistent with medical practice.

Registration readers will also have access to the results of two locked nomograms to separately predict the POM and the probability of cancer. These nomograms were constructed from the Pilot Study cases using a linear model for the POM and a logistic regression model for the probability of cancer. The nomograms are constructed from the five feature scores for Imagio from a blinded review performed by [name]. The registration readers do not need to use the results of the nomograms in making their POM judgments, but they will immediately see the two predictions as soon as they score the five

features. The sensitivity and specificity of the nomograms will also be evaluated using the average predicted score; if the average is ≤ 0.1 , then the case is predicted to be benign.

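### Registration readers are shown two fitted nomogram predictions on the Imagio read but none on the IUS read, and no planned read separates this aid from the opto-acoustic images

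*Protocol*

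**What the plan says.** Protocol section 8.1.1 states: "Registration readers will also have access to the results of two locked nomograms to separately predict the POM and the probability of cancer". On their origin: "These nomograms were constructed from the Pilot Study cases using a linear model for the POM and a logistic regression model for the probability" (that is, of cancer). Their inputs are opto-acoustic: "The nomograms are constructed from the five feature scores for Imagio from a blinded review performed by" a named reviewer.

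On use and timing, the same section says "The registration readers do not need to use the results of the nomograms in making their POM judgments, but they will immediately see the two" model outputs; the display comes once the reader has finished scoring the features. It does not say when the Imagio POM is entered or locked relative to this display.

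For IUS, section 8.1.1 gives readers a separate pre-determined rule set and mentions no fitted prediction. It also requires the IUS evaluation to be locked before the Imagio evaluation of the case begins.

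The primary endpoint is specificity at a 2% POM (8.1.1). H1 and H2 compare Imagio with IUS on specificity and sensitivity. H5 and H6 compare BI-RADS between the same two reads (8.2.1, 8.2.2, 8.2.5, 8.2.6). Sections 3.1 and 5.8 describe the Imagio image set as diagnostic ultrasound plus opto-acoustics. Section 5.1 lists probe, laser, electronics, ultrasound and software, and of the last it says: "The software controls the overall data flow from the data acquisition process to the display of the final co-registered OA and diagnostic ultrasound images". Neither section 5.1, the objectives in section 2 nor the hypotheses in 8.2 mention a nomogram.

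Section 8.7.1 plans a separate evaluation of the nomograms' own sensitivity and specificity, at a cut of 0.1.

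**The concern.** Two things change between the IUS read and the Imagio read. The reader gains the OA images, which is the stated comparison. The reader also gains two model outputs, one of which predicts the very quantity that is cut at 2% to form the primary endpoint. Both reads have a rule set, so the fitted prediction is the asymmetry.

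If the displayed predictions influence the POM, a specificity difference is the joint result of images and aid. The PMA filing rests on these reads (8.1.1), and the claim it would support concerns the modality described in section 5.1. Making use optional does not make the display optional, and the protocol provides no record of whether a reader used the predictions. This is a matter of data capture: a POM formed before display cannot be recovered later by any analysis if it was never recorded.

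**Working it through.** **1. What differs between the two reads**

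| | IUS read | Imagio read |
|---|---|---|
| Images | ultrasound | ultrasound plus OA |
| Rule set | yes | yes |
| Fitted prediction shown | none stated | two (POM, probability of cancer) |
| Lock stated | before the Imagio read begins | none stated before the predictions appear |

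The nomogram analysis in 8.7.1 scores the averaged prediction against truth. It yields no reader POM formed without the prediction, so it does not fill the gap.

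**2. Table 6 reproduced**

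Inputs (section 8.6, Table 6): difference d = 0.06, discordance η = 0.20, power 90%, n = 860. The 0.5% level is read as one-sided, in line with the one-sided 99.5% bound in 8.7.1, so z = 2.576.

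- n = [(z_α√η + z_β√(η − d²))/d]² = [(2.576 × 0.4472 + 1.2816 × 0.4432)/0.06]² = 822.
- With continuity correction: (822/4) × [1 + √(1 + 4/(822 × 0.06))]² = 855, close to the stated 860.
- Uncorrected power at 860 is 91.5%.

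The sample size is not in question. It supplies the scale for what follows.

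**3. Observed difference that meets the H1 bound**

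The lower bound exceeds 0 once d > 2.576 × √((0.20 − d²)/860). Solving gives d = 0.0391, or 0.0391 × 860 = 33.7, about 34 masses.

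**4. Chance of winning H1 from the nomogram alone**

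The protocol gives no nomogram effect. Assume the images add nothing and the display adds a true net gain d in specificity, varied from 0 to 6 points. Then

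P = Φ[(d√n − z√η)/√(η − d²)], with √860 = 29.33 and z√η = 1.152.

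- d = 0.03: (0.880 − 1.152)/0.4462 = −0.610, P = 27%
- d = 0.04: (1.173 − 1.152)/0.4454 = 0.047, P = 52%
- d = 0.06: (1.760 − 1.152)/0.4432 = 1.371, P = 91%

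At d = 0 the figure is the nominal 0.5%. At n = 1,000, the protocol's minimum number of benign masses, the three become 32%, 60% and 95%.

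These are single-pair McNemar figures. The planned analysis is a generalized linear model across seven correlated readers (8.7.1), so the 3.9-point threshold is not the trial's own.

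**The case against.** The strongest reply is that the aid is itself opto-acoustic. The nomograms are built on five Imagio feature scores and are displayed when the reader scores those features; no clinical, mammographic or IUS variable is named as an input. On that view a gain is OA content combined by fixed weights, and structured interpretation is already part of both reads. Section 5.1 does not list the reader rule sets either, so its silence on the nomogram proves little. This stands in part: images and statistics are not cleanly opposed, and the sponsor could legitimately regard the nomogram as part of Imagio. But the weighting is a model fitted to Pilot cases, IUS receives no counterpart, and the protocol nowhere says that Imagio includes it.

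Timing is also inferred. The text ties the display to feature scoring and contemplates use in the POM judgement, but it does not say when the POM is entered, and a separate imaging committee protocol (9.8) governs the review process. A reader might infer that every Imagio POM is anchored by the predictions. The documents support only that it may be formed with them visible.

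A reader might also infer that the aid inflates specificity. The direction is unknown. The nomogram's own benign cut is 0.1, so a prediction it calls benign can lie above the 2% threshold and could push a benign mass to the positive side.

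The protections are real. The nomograms are locked and fitted only to Pilot cases, which are excluded from the registration analysis, so overfitting to Pivotal data is not at issue. The earlier IUS lock keeps the aid out of that case's IUS score.

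**Conclusion.** The point holds as one of attribution. As written, a difference in H1, H2, H5 or H6 may combine the OA images with a fitted aid that only the Imagio read receives, and the planned reads cannot separate them. This rests on the inference that the POM can be entered after the predictions appear; no lock rules that out.

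The size is not known. The 27%, 52% and 91% figures assume 20% discordance, 860 benign masses, one read per mass, no image effect, and a shift that favours Imagio. They show that an effect smaller than the planned 6 points could matter, not that one exists. A reader might conclude that a 4-point nomogram shift makes H1 succeed. That is true only of an observed difference, which exceeds the 3.9-point threshold; a true 4-point shift succeeds about half the time. Nor do the documents support saying that the comparison is invalid or that OA imaging contributes nothing.

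**What to change.** In section 8.1.1 and the reader eCRF, require the reader to lock an Imagio POM and BI-RADS after scoring the features and before the nomogram predictions appear. Then allow a second POM and BI-RADS after display. Report H1, H2, H5 and H6 for both.

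State in advance which is primary:

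- the pre-nomogram read, if Imagio means ultrasound plus opto-acoustics as now described; or
- the post-nomogram read, only if the device description and the hypotheses are reworded to include the nomogram.

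The cost is a few seconds per read, one eCRF change and possibly a less favourable headline figure. The protocol already locks IUS before Imagio, so the extra step follows an existing pattern, and the nomogram-aided result remains available.
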